Data from the Diabetes Control and Complications Trial (DCCT) demonstrated that lowering the A1c by intensive insulin management to near-normal glycemic levels decreases the risk of complications related to diabetes (6). However, intensive management in the DCCT was accompanied by marked increases in severe hypoglycemia and more recent data have implicated increased insulin doses as risk factors for cardiovascular disease in T1D (7). One approach to achieve targeted glycemic control with less insulin exposure is through the use of a very low carbohydrate diet (VLCD), defined as limiting carbohydrate intake to 50 grams per day or less (8). In adults with T1D, these diets have been shown to achieve exceptional glycemic control with physiologically normal A1c values with lower total daily insulin doses due to decreased mealtime insulin for low amounts of carbohydrate intake (9, 10).

Importantly, VLCDs have not been formally studied in adolescents and young adults with T1D. Observational data on children using a VLCD are also conflicting. A small case series of 6 children with T1D on a low carbohydrate diet showed deficits in anthropomorphic measurements and elevated lipids, though in some cases a caloric deficit was also reported (11). Conversely, a recent observational study of 131 children with T1D on a VLCD reported no significant change in height percentile or SDS after initiating the diet (12). Prior studies have explored use of low carbohydrate diets in T1D, but none have specifically monitored for ketosis. In those studies, it is likely that the lack of carbohydrate intake led to lower insulin needs, thus increasing lipolysis and ketogenesis, and levels of ketosis while on this type of diet require further study (13).

Page 2 of 26

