Research Plan: This prospective feasibility study of 10 youth (ages 13 – 25) with T1D will evaluate glycemic and metabolic changes after 2 weeks of a high protein VLCD compared to 2 weeks on a standard carbohydrate diet (see Table 1). The study will take place in 2 parts. Part 1 will only involve the high protein VLCD, but part 2 will involve high protein VLCD and high fat VLCD's.

| Type of Diet | Carbohydrates | Protein | Fat |
|-------------------|---------------|---------------|---------------|
| Standard | 25%+ | Not specified | Not specified |
| Carbohydrate | | | - |
| High Protein VLCD | 11% | 54% | 35% |
| High Fat VLCD | 11% | 23% | 66% |

Table 1. Types of study diets and macronutrient content in each planned diet.

Part 1: First, to evaluate the feasibility of following a high protein VLCD, participants will follow a standard carbohydrate diet for 2 weeks, followed by a 1 week transition to a VLCD, and then follow the a high protein VLCD for 2 weeks. The study will consist of 3 in person or virtual visits which will take place over ~5 weeks. All participants will be initially studied for 2 weeks while ingesting a standard diet recommended by the American Diabetes Association, followed by a 1-week transition to a VLCD, and followed by 2 weeks on the high protein VLCD. During the first (baseline) period fasting β -hydroxybutyrate levels will be measured 2-3 times per week. During the VLCD study periods, fasting β -hydroxybutyrate levels will be measured daily in the morning using a blood ketone meter; insulin doses will be collected using insulin pump downloads and continuous glucose monitoring (CGM) profiles will be used to assess glycemic excursions on each diet, as

[figure not shown]
Page **3** of **26**

well as the time in hypo-, eu- and hyperglycemic ranges. Part 1 of the study is anticipated to be complete by December 31, 2022.

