5. **Participants**: This study will enroll 10-20 participants (ages 13 to 25) with T1D. At least 4 adults over the age of 18 will be enrolled. Ten youth will be involved in Part 1, which evaluates feasibility of the diet. If those youth would like to continue to Part 2 of the study they may continue, or they will be replaced by new participants. To be eligible for inclusion, the participant must have T1D for at least 1 year, have an A1c between 6.5% to 10.0% inclusive, and BMI of at least 19 kg/m2 (or 5th percentile for those under age 18) and be willing to wear a CGM, which is the currently recommended standard of care for children with type 1 diabetes and is FDA approved for use above age 2 years. They must also be willing to adhere to a VLCD, measure β -hydroxybutyrate levels daily and to keep a detailed food diary. Participants who are unable to wear a CGM, monitor their diabetes control or maintain the VLCD will be replaced.

Study visits: Participants will be recruited from Yale Pediatric Diabetes Center and Yale Diabetes Center clinics, as well as through social media. All participants will undergo pre-screening of their electronic medical record (or faxed medical record from their pediatric endocrinologist or endocrinologist) to evaluate study eligibility by review of medical history, as well as prior physical exams and laboratory tests. No blood will be collected in part 1 of the study.

Figure 1. Timeline of visits and telephone follow ups for the duration of the study. Visits and calls may be modified depending on patient availability and academic schedule. Part 1 of the study will involve in-person or virtual visits (Facetime, Video Doximity Calls, Zoom, or Skype) and telephone study visits. Part 2 of the study will involve in-person visits.

Screening & Enrollment Visit 1: Screening will be conducted by invitation to potentially eligible subjects. For the first part of the study, the study will be explained and telephone or e-consent will be obtain prior to conducting any study procedures. Participants will 1) meet in person or 2)use telephone to discuss the study or 3) Skype, Zoom, FaceTime or Doximity Dialer enabling video calls. Scales will be provided for all participants.

Consent: Consent will be transitioned to an online/electronic format using the YSM version of REDCap if consent is not obtained in person.

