- Point of care HbA1c, obtained via fingerstick and measured by a Seimens DCA Vantage device, will be determined unless an A1c was measured in clinic within the past 30 days.
- Current diabetes care practices (frequency of self-monitored blood glucose (SMBG), insulin dosing, review of blood glucose values)
- Medical History: duration of diabetes, comorbidities, past medical history, social history, family history, medications, and allergies.
- Additional diabetes history including current/past use of CGM, insulin pump, and other modes of diabetes technology.
- Frequency of missed school days and Emergency Department visits due to decompensated diabetes (i.e., hyperglycemia, ketosis and DKA) over the past 6 months
- Baseline laboratory assessment if it has not been done in the past year, as a part of standard of care (comprehensive metabolic panel with electrolytes, lipid panel, urine microalbumin).
- Questionnaires will be administered, including:
 - a. Diabetes Treatment Satisfaction Questionnaire (DTSQ), which includes eight items, six of which form a scale (scored 0-36) in which higher scores indicate greater treatment satisfaction (Bradley, 1994).
 - b. Nutrition Knowledge Survey (NKS) which collects information on healthful eating, carbohydrate counting, blood glucose response to foods, and nutrition label reading. Higher NKS scores reflect greater nutrition knowledge (score range is 0–100%) (Rovner 2012).
 - c. Diabetes Distress Scale (DDS) is a 17-item scale that captures diabetes distress in 4 different areas, including emotional burden, regimen distress, interpersonal distress, and physician distress (Polonsky 2005).

All participants will receive dietary instruction to review the dietary requirements of the study. A handout with 2 examples of the type of diet required will be provided to each participant at the time of or prior to consent. Participants will provide a 3-day dietary history at the enrollment visit to assess current caloric intake. Each subject will be instructed on how to keep a food diary. Participants and/or parents will be asked to take photos of all food consumed to aid in dietary recall. After the enrollment visit, participants will be contacted to assess adherence to the diet and adjust insulin doses 3 times per week (see Table 1). During these telephone follow up calls, food diary will be reviewed, photos of meals will be reviewed, and pump and CGM data will be uploaded and reviewed.

Page 7 of 26

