Prior to the HRU/CSRU admission, we will recommend a standard diet be given and no food be eaten after 9pm (except for in cases of hypoglycemia). Participants will be advised to limit exercise in the 3 days prior to study to limit acute effects of recent exercise on insulin sensitivity.

Visit 2: After at least 2 weeks on the standard carbohydrate diet, participants will be admitted to the HRU or CSRU for the equilibration portion of the study and arginine stimulation test. The subject may arrive at 7:30 a.m. the morning of the study. The study nurse will do a nursing assessment, including measuring the subject's temperature, blood pressure, and pulse. A urine pregnancy test will be performed and we will discuss the need for contraception during the VLCD portion of the study. Two indwelling catheters will be placed, one into an antecubital vein for infusion of test substances and a second catheter into a contralateral vein for blood sampling.

The study will begin with a ~150 minute equilibration period during which we will aim to keep glucose levels stable, followed by an arginine stimulation test. Blood draws for measurements of glucose and glycerol enrichment are listed in tables 2, 3, and 4.

Subjects will be asked permission to allow the serum and information collected during this research study to be used for future research purposes. The serum samples may be used by our research group to run additional assays related to the pathophysiology of diabetes.

- *Fasting laboratory assessment:* Upon arrival, participants will have blood tests performed, including *β*-hydroxybutyrate, free fatty acids (FFA), glucagon, comprehensive metabolic panel, magnesium level.
- Non-radioactive, Stable Isotope Tracer Infusions will be employed to assess rates of glucose and glycerol metabolism at the end of the ~150-minute baseline equilibration period. From -150 to 0 min, 4.5 mg/kg of 6,6-²H₂-glucose (99% enriched; Cambridge Isotope Laboratories, Andover MA) will be followed by a continuous infusion at 0.06 mg/kg/min. ²H₅₋ glycerol will be infused at 1.6 µmol/kg followed by a constant infusion of 0.11 µmol/kg/min to assess glycerol turnover. During the basal turnover period, a variable rate insulin infusion may be utilized to maintain plasma glucose between ~80-120 mg/dL. As results from prior participants become available, infusions of the isotopes may be adjusted in subsequent participants to ensure enrichment is not too low for measurement.

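### No lipid panel is scheduled on any study diet, although the background cites raised lipids in children on carbohydrate restriction and one Part 2 diet is 66% fat

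*Combined protocol and SAP*

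**What the plan says.** Section I, item 4 (Background) describes a case series of 6 children with type 1 diabetes on a low carbohydrate diet that "showed deficits in anthropomorphic measurements and elevated lipids, though in some cases a caloric deficit was also reported". The aims in the same item include metabolic changes and safety measures of the diet. The diet table in the Research Plan gives the Part 2 high fat VLCD 66% of its content as fat, against 35% for the high protein VLCD. Part 2 randomises participants between the two and states no allocation ratio.

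Blood tests are placed as follows.

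- Part 1 (item 5, Study visits): "No blood will be collected in part 1 of the study".
- Part 2, Screening & Enrollment Visit: a baseline set, which contains the lipid panel, is drawn only if not already "done in the past year, as a part of standard of care (comprehensive metabolic panel with electrolytes, lipid panel, urine microalbumin". The Part 2 schedule marks it at week 0 only.
- Part 2, Visit 2, Fasting laboratory assessment, taken on arrival: β-hydroxybutyrate, then "free fatty acids (FFA), glucagon, comprehensive metabolic panel, magnesium level".
- Part 2, Visit 3: the Visit 2 procedures are repeated.

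Item 13 (Statistical Considerations) names no lipid outcome. Its safety analysis covers diabetic ketoacidosis and severe hypoglycaemia.

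**The concern.** The plan brings up raised lipids in children as a reason for caution, then brings participants in fasting at the end of each Part 2 diet period and does not run the test that bears on it. The one lipid value it does obtain comes before both diet periods and may be a clinic result from up to a year before enrolment.

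At stake is a safety description. The protocol rates itself as greater than minimal risk, for children as well as adults, and assigns some participants to a diet that is two-thirds fat. From the planned tests, the report could say nothing about cholesterol or triglycerides on either VLCD, and the investigators would not see an individual's values during the study.

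**Working it through.** The documents give no sample size or power calculation to reproduce. The check is of the measurement schedule first, then of what the remedy would yield, then of the blood it would need.

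**1. Lipid panels by time point**

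| Time point | Blood taken | Lipid panel |
|---|---|---|
| Part 1, all visits | none | none |
| Part 2, week 0 | baseline set, if none in past year | yes, or an existing result |
| Part 2, end of week 2 (Visit 2, standard diet) | fasting set, tracer and arginine samples | none |
| Part 2, end of week 5 (Visit 3, VLCD) | same as Visit 2 | none |

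A within-person change on the VLCD needs at least one panel after the diet starts. The planned number is 0 in Part 1 and 0 in Part 2.

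Age of the only value at Visit 3: at least 5 weeks, and up to 52 + 5 = 57 weeks. It may reflect the participant's usual diet and not the study's standard diet.

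**2. Precision if panels are added at Visits 2 and 3**

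Half-width of the 95% confidence interval for the mean paired change, in SDs of that change: t(0.975, n−1)/√n.

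- n = 10 (both diets pooled): 2.262/3.162 = 0.715
- n = 5 (one diet, equal allocation assumed): 2.776/2.236 = 1.242
- n = 4 (one diet, if allocation is uneven or a pair is lost): 3.182/2 = 1.591

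Mean change detectable with 80% power at two-sided 0.05 (both my assumptions; paired t-test, noncentral t): 1.00 SD for n = 10 and 1.68 SD for n = 5. This supports description, not testing.

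**3. Blood volume**

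Table 4, per visit: 36 + 51.5 + 11 + 24 = 122.5 mL, which reproduces the table's total. The 11 mL is the fasting laboratory draw.

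Visits 2 and 3 are 3 weeks apart, so both fall inside one month: 2 × 122.5 = 245 mL.

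- Adults: the cap in item 11 (Risks, Anemia) is 250 mL over a month. This leaves 5 mL, or 2.5 mL per visit. A 3 mL tube at each visit would bring the total to 251 mL.
- Under 18: the cap is 5 mL/kg over a month. 245/5 = 49 kg, so a minor below 49 kg would already exceed it. At 40 kg, the lowest weight in Table 4, the total is 245/40 = 6.1 mL/kg. Table 4 shows about 3 mL/kg because it counts one visit.

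**The case against.** The strongest case against is that this asks for an outcome the study never promised. The aims name glucagon, β-hydroxybutyrate, free fatty acids, hepatic glucose production, glycerol turnover and lipid oxidation, and the safety measure they name is daily fasting ketones. The VLCD is isocaloric and lasts about 2 weeks after a transition week, whereas some children in the cited series had a caloric deficit. On this view, leaving out cholesterol in a pilot of 10 is a preference. It is right that no planned analysis becomes wrong. What remains is that the rationale raises the harm and the fasting visits already take place.

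Several stronger readings are tempting, and the documents do not support them.

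- A reader might infer that fat metabolism goes unmeasured on the diets. Free fatty acids, glycerol turnover and fat oxidation are all measured at Visits 2 and 3. The gap is the lipid panel.
- A reader might infer that a lipid change could never be recovered. The fasting list is introduced as non-exhaustive, and serum is stored at both visits with permission sought for further assays. No lipid assay is planned, however, and a later research assay would not give timely safety information.
- A reader might infer that half of Part 2 eats the 66% fat diet. The allocation ratio is not stated.
- A reader might infer that 10 pairs are enough to detect large individual rises. The 0.72 SD figure is the precision of a mean pooled over two different diets. One pair per person cannot separate a diet effect from ordinary within-person variation.
- A reader might infer that stored serum makes the remedy free. The storage samples timed in Table 3 are drawn from 15 minutes before to 60 minutes after arginine, when the tracers, and possibly insulin, have been infused for over two hours. They are also held for permission-based future research.

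**Conclusion.** The point holds in this form: the planned tests cannot show a within-person change in cholesterol or triglycerides on either VLCD, for any participant in either part. This follows from the schedule alone and rests on no statistical assumption.

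It is an inexpensive improvement worth making, not an error in an existing analysis. The documents give no basis for expecting a particular lipid change within two weeks, and the cited series is small and partly confounded by caloric deficit. The half-widths assume complete pairs and, for the per-diet figure, 5 participants on each diet.

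Separately, the Table 4 volumes summed over two visits conflict with the protocol's own cap for minors under 49 kg and leave adults only 5 mL. Those passages need reconciling whether or not lipids are added.

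**What to change.** - In Part 2, add a lipid panel to the Fasting laboratory assessment at Visits 2 and 3, with a matching entry in the schedule. Run it on the fasting arrival sample (the 11 mL draw), not on the Table 3 storage samples.
- The documents do not say whether the 11 mL has volume to spare. If it does not, reduce another draw by the same amount so that the total does not rise.
- Reconcile Table 4 with the blood volume limits under Anemia in item 11, both in Risks and in Minimizing Risks, counting both visits.
- In item 13, list the paired Visit 3 minus Visit 2 lipid change as a descriptive safety outcome, with individual values shown by diet. State that it reflects short-term change only.

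Cost: about 20 assays (10 participants × 2 visits), no extra venepuncture, and slightly less blood for other uses. Part 1 would still have no lipid data, since it draws no blood.

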Upon completion of the AST, participants will meet with study staff to review the requirements of the transition week and VLCD portion of the study. The dietician will look at each individuals macronutrient intake during the standard carbohydrate portion of the study. Based on this information, we will instruct them to eat a certain amount of carbohydrates each day. If they eat more than 200 grams per day of carbohydrates during the standard diet weeks, they will be instructed to eat 100-150 grams of carbohydrates per day during the transition week. If they eat less than 200 grams per day of carbohydrates during the standard diet weeks, we will instruct them to eat 75-125 grams of carbohydrates per day during the transition week. Most people with diabetes know how to carbohydrate count, however we will review carbohydrate counting at the time of the transition. Carbohydrate counting will be taught using the "Choose Your Foods: Food Lists for Diabetes" written by the American Diabetes Association and the American Nutrition of Dietetics.

For the VLCD portion of the study, participants will be given an isocaloric diet with a goal carbohydrate intake of less than 20% carbohydrates per day (~100 grams per day) for adolescents and less than ~50 grams per day for adults at least 18 years of age. Guidelines will be provided for meals. Participants will also receive training on the treatment of hypoglycemia and be instructed to call the study team immediately in the case of severe hypoglycemia.

Visit 3: After at least 2 weeks on the very low carbohydrate study diet, participants will be admitted to the HRU/CSRU and repeat the same protocol listed in Visit 2.

| Measurement | Wk 0 | Phone wk 0.5 | Phone wk 1 | Phone wk 1.5 | Visit end wk 2 | Transition to VLCD wk 2-3 | Phone wk 3 | Phone wk 3.5 | Phone wk 4 | Phone wk 4.5 | Visit end wk 5 |
|---|------|-----------------|---------------|-----------------|----------------------|---------------------------------|---------------|-----------------|---------------|-----------------|----------------------|
| Dietary Recall, assessment for symptoms related to VLCD | x | х | х | x | x | х | x | х | х | х | х |
| Diabetes management review, dose adjustments as needed, CGM data analysis | х | х | x | x | x | х | x | x | x | х | x |
| Baseline laboratory assessment | х | | | | | | | | | | |

Table 1. Planned study interventions for part 2 of the study.

HIC#: 2000026189

| Fasting laboratory assessment | | | х | | | х |

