|---|---|--|---|--|--|---|
| Stable isotope study of glucose and glycerol metabolism, indirect calorimetry, arginine stimulation test | | | x | | | x |
| Diabetes Treatment Satisfaction Questionnaire | x | | х | | | х |
| Diabetes Treatment Satisfaction Questionnaire (Change) | | | | | | x |
| Nutrition Knowledge Questionnaire | х | | х | | | х |
| Diabetes Distress Scale | Х | | Х | | | Х |

Table 2. Planned blood tests during the baseline glucose and glycerol turnover study.

| Time (minutes) | -150 | -120 | -90 | -60 | -30 steady state | -15 steady state |
|---------------------|------|------|-----|-----|------------------------|------------------------|
| Glycerol (2mL) | x | X | X | X | X | x |
| Glucose (0.5 mL) | X | X | X | X | X | X |

Table 3. Planned blood tests during arginine stimulation testing. Time 0 represents time of Arginine infusion.

| Time | -15 | 0 | 5 | 15 | 30 | 45 | 60 |
|-------------|-----|---|---|----|----|----|----|
| (minutes) | | | | | | | |
| ВОНВ (0.3 - | X | X | X | X | X | X | X |
| 1mL vs use | | | | | | | |
| meter) | | | | | | | |
| Glucose | X | Х | X | X | X | X | X |
| (0.5mL) | | | | | | | |
| Glucagon | X | Х | X | X | X | X | X |
| (2mL) | | | | | | | |
| C-peptide | | X | | | X | | X |
| (3mL) | | | | | | | |

PI: [name]

HIC#: 2000026189

| Storage | X | X | X | X | X | X | X |
|---------|---|---|---|---|---|---|---|
| (3mL) | | | | | | | |

| Weight (kg) at Blood Draw | Equilibration | Arginine stimulation Test | Fasting laboratory assessment | Storage (Serum) | Total Blood Volume Collected (mL) | Total Blood Volume Collected (mL/kg) |
|------------------------------|---------------|---------------------------------|-------------------------------------|--------------------|--|---|
| 40 to 42 | 36 mL | 51.5 mL | 11 mL | 24 mL | 122.5 | ~3 |
| 43 to 65 | 36 mL | 51.5 mL | 11 mL | 24 mL | 122.5 | 1.9-2.8 |
| >65 | 36 mL | 51.5 mL | 11 mL | 24 mL | 122.5 | <1.9 |

Table 4. Blood volume collected during each HRU visit.

6. Genetic Testing N/A 🛛

7. Subject Population:

Part 1: 10 participants ages 13 to 25 years of age with a clinical diagnosis of T1D for at least 1 year will be enrolled for 5-6 weeks for part 1 of the study. Participants who reach the age of majority during the study will be re-consented using the adult consent form.

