- Risk of indwelling catheter: There are potential complications associated with indwelling catheters, including hematomas, discomfort, and rarely infection, thrombophlebitis, or bleeding at the catheter insertion site.
- Anemia: The risk of anemia exists in studies with frequent blood draws. In our many years of performing studies we have not known any participants to experience this complication. The volume of blood draw at each visit will vary depending on the participant's age and weight. However, for children <18 years the maximum blood volume will not exceed 5 cc/kg body weight over a 1-month period. The exact blood volumes collected may vary according to local IRB regulations. The maximum blood volume collected from adults >18 years will not exceed 250cc over a 1-month period.
- Risk of loss of confidentiality: As in any study, there is the potential for loss of confidentiality. Female subjects of childbearing potential will require urine pregnancy testing prior to enrollment in the protocol, and results of this testing have potential to result in loss of confidentiality.
- Risk of glycemic deterioration: It is possible that changing dietary requirements or insulin doses may result in glycemic deterioration. Likewise, adolescents may have glycemic deterioration due to non-compliance.

Page 12 of 26

- Risk of CGM: Participants have the option of using FDA approved CGM as part of clinical care in our clinics. There is a low risk of developing a local skin infection at the site of the sensor needle placement. Itchiness, redness, mild bleeding, and or bruising may occur at the insertion site. Subjects may develop localized reactions to adhesive used to secure the sensor.
- Risk of study questionnaires: Participants may experience some distress when discussing factors important to diabetes, diabetes management, and psychosocial stressors
 - Arginine Stimulation Test: Intravenous infusion of glucose may cause venous irritation (phlebitis) or less commonly infiltration of the surrounding tissues, both which may be discomforting. Intravenously administered arginine may cause a transient metallic taste in the mouth, and less often a transient sensation of warmth or nausea; allergy is rare.

Minimizing Risks:

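### Part 2 blood volumes are shown per visit while the cap for minors is monthly: Table 4 as printed totals 245 mL over two admissions, above the cap below 49 kg, unless its storage column is a double count

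*Combined protocol and SAP*

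**What the plan says.** Only Part 2 draws blood; the Part 1 text says none is collected there.

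- **Cap.** Section I, item 11 (Risks), Anemia: "for children <18 years the maximum blood volume will not exceed 5 cc/kg body weight over a 1-month period". Adults are limited to 250 mL over the same period. The Anemia item under Minimizing Risks repeats both limits without a time window. The Risks paragraph also says the draw will depend on age and weight.
- **Volumes.** The caption reads "Table 4. Blood volume collected during each HRU visit". The lightest row is "40 to 42 | 36 mL | 51.5 mL | 11 mL | 24 mL | 122.5 | ~3" and the heaviest is ">65 | 36 mL | 51.5 mL | 11 mL | 24 mL | 122.5 | <1.9". The volume is the same in all three rows; only the mL/kg column changes.
- **Repetition.** At Visit 3, "participants will be admitted to the HRU/CSRU and repeat the same protocol listed in Visit 2". The Part 2 schedule (Table 1) places the two admissions at the end of week 2 and the end of week 5.
- **Itemised draws.** Table 2 lists glycerol and glucose samples at six times. Table 3 lists the arginine-test samples and has its own storage row, "Storage | X | X | X | X | X | X | X", at 3 mL each.
- **Eligibility.** Participants may be as young as 13. Minors need a BMI above the 5th percentile, but no minimum weight is set.

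**The concern.** The limit is monthly and the table is per visit. Someone checking the printed value of about 3 mL/kg against 5 would conclude that the lightest participants are well within the limit. With two identical admissions inside a month, the quantity to compare with the cap is twice the printed figure, and the plan shows it nowhere.

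Table 4 is also the only place where the draws are totalled, and its components do not follow from Tables 2 and 3. At stake is a stated safety limit for minors, in a study the investigators themselves rate as greater than minimal risk. No estimate or test depends on it.

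**Working it through.** **1. Reproduce Table 4.** Visit total: 36 + 51.5 + 11 + 24 = 122.5 mL, as printed. Per visit: 122.5/40 = 3.06, 122.5/42 = 2.92, 122.5/43 = 2.85 and 122.5/65 = 1.88 mL/kg. These match the printed column, so the table is correct on its own per-visit basis.

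**2. Interval.** End of week 2 to end of week 5 is 3 × 7 = 21 days. If enrolment runs to the 6 weeks mentioned in item 7, the gap is 42 − 14 = 28 days. Both lie within a month.

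**3. Two admissions as printed.** 2 × 122.5 = 245 mL. The lowest weight that meets the cap is 245/5 = 49 kg. Below that: 245/40 = 6.1, 245/42 = 5.8 and 245/43 = 5.7 mL/kg. The whole 40 to 42 kg row exceeds the cap, as does the next row up to 49 kg. Adults would stand at 245 of 250 mL.

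**4. Table 4 against Table 3.** Volumes times number of samples:

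- β-hydroxybutyrate: 7 × (0.3 to 1) = 2.1 to 7 mL
- glucose: 7 × 0.5 = 3.5 mL
- glucagon: 7 × 2 = 14 mL
- C-peptide: 3 × 3 = 9 mL
- storage: 7 × 3 = 21 mL

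Without storage the sum is 28.6 to 33.5 mL; with it, 49.6 to 54.5 mL. Table 4's 51.5 mL lies inside the second range and far above the first. It implies (51.5 − 47.5)/7 = 0.57 mL per β-hydroxybutyrate sample, within the stated 0.3 to 1 mL. Equally, 1 mL samples with storage at six times give 33.5 + 18 = 51.5 mL exactly. The arginine figure therefore probably includes storage already.

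**5. Table 4 against Table 2.** Six samples of 2 + 0.5 mL make 15 mL, against 36 mL in Table 4. The Metabolite Collection text mentions hormone and substrate samples that Table 2 does not list. They may explain the gap, but no volumes are given.

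**6. Range of readings.** Lowest compliant weight = two-admission total/5.

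| Reading | Per visit (mL) | Two admissions (mL) | mL/kg at 40 kg | Cap met from (kg) |
|---|---|---|---|---|
| (a) Table 4 as printed | 122.5 | 245 | 6.1 | 49 |
| (b) Storage counted once, inside 51.5 mL | 98.5 | 197 | 4.9 | 39.4 |
| (c) As (b), plus the unexplained 24 − 21 = 3 mL | 101.5 | 203 | 5.1 | 40.6 |
| (d) Tables 2 and 3 itemised, plus 11 mL fasting laboratory | 75.6 to 80.5 | 151 to 161 | 3.8 to 4.0 | 30.2 to 32.2 |

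Table 3 also allows a meter for β-hydroxybutyrate. If that takes negligible blood (an assumption), (d) falls to 15 + 47.5 + 11 = 73.5 mL per visit, 147 mL in all, and a threshold of 147/5 = 29.4 kg.

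**The case against.** The strongest reply is that the cap is an explicit maximum and overrides a listed volume. The Risks text says volumes vary with age and weight and may follow local IRB rules; Minimizing Risks promises minimum necessary draws and adherence to the limit. This makes an actual breach avoidable. It does not repair the table, which prints one fixed volume at every weight and does not say which samples to drop for a light minor.

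Second, the 49 kg threshold comes from the reading that Tables 2 and 3 make least likely. Under (b) and (d) every printed weight row complies, and under (c) only weights from 40 to just under 40.6 kg fail. This stands, and it is why the breach is stated conditionally. But if (b) or (d) is right, Table 4 is wrong as a record of what will be drawn. The documents do not settle the matter: the Metabolite Collection text also plans additional baseline samples, which could be a separate stored draw.

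Third, each diet lasts at least two weeks and visits may be moved, so 28 days is not a firm ceiling. The 5-to-6-week figure in item 7's Part 2 paragraph also refers literally to Part 1. Both points are fair, but the planned gap is three weeks, and the second statement of the cap has no time window.

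Finally, few or no participants may be light enough to matter. That is also fair, although the table's own 40 to 42 kg row shows that such weights were foreseen.

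**Conclusion.** The concern holds. Table 4 is not on the basis on which the cap is set, and the volumes it prints cannot meet the cap for a minor under 49 kg (245 mL; 6.1 mL/kg at 40 kg). This rests on Table 4 being correct as printed and on the admissions falling within a month, as scheduled. If the storage column repeats blood already in the 51.5 mL, the total is 197 mL and all printed rows comply, but then the table misstates the draw. Either way it needs correction.

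The defect in the table is certain; a breach is not. The documents give no weight distribution, so the number of minors under 49 kg among the 10 Part 2 participants is unknown and could be zero. Minors under 40 kg are eligible but have no row. No planned analysis changes. This should be fixed before Part 2 enrols minors.

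**What to change.** 1. Reconcile Table 4 with Tables 2 and 3. State whether 51.5 mL includes the stored samples and, if so, delete the 24 mL column. List the equilibration samples that make up 36 mL.
2. Replace the per-visit mL/kg column with the two-admission total, and set volumes by weight so that it stays at or below 5 mL/kg.
3. If Table 4 is right as printed, omit the 24 mL storage draw at both admissions for minors under 49 kg. That leaves 2 × 98.5 = 197 mL, which meets the cap from 39.4 kg.
4. Below that weight, state a further reduced volume or set a minimum weight for Part 2.

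The cost is a correction to one protocol table and, at most, some stored serum from the lightest minors. Stored serum is kept by permission for future research, so no planned analysis and no Visit 2 to Visit 3 comparison loses data.
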